If ≥ 2 patients develop the same CTCAE grade 3 adverse event or 1 patient develops a CTCAE grade 4 adverse event, the study will be suspended until the DSMB reviews the events and makes a determination whether to continue. If a Grade 3 or worse event is clearly attributable to a non-treatment event and therefore not a suspected adverse reaction: [21CFR312.32(a)] the event will not be considered for the purposes of stopping.

Number of patients: up to 28 patients are planned for inclusion, 14 in each vision cohort

Diagnosis and main criteria for inclusion:

Inclusion Criteria

The following conditions must be met before a subject may be enrolled in the study.

- 1. Willing to give written informed consent, able to make the required study visits and follow study protocol instructions.
- 2. Willing to consent to gene mutation typing. Mutation typing will be restricted to typing for eye disease-related genes known to be involved in inherited retinal degenerations and related disorders. If typing results are already available for the subject, the previous results can be recorded and this requirement is waived.
- 3. Clinical diagnosis of RP confirmed by ERG.
- 4. BCVA 20/200 or worse and no worse than HM in cohort 1; and BCVA 20/40 or worse and no worse than 20/200 for the second cohort.
- 5. Male or female, age ≥ 18 yr.
- 6. Adequate organ function:
 - blood counts (hematocrit, Hgb, WBC, platelets and differential) within normal range, or if outside of normal range, not clinically significant as judged by the investigator
 - \circ liver function: alanine transaminase [ALT] and aspartate transaminase [AST] ≤ 2 times the upper limit of the normal range
 - \circ total bilirubin ≤ 1.5 times the upper limit of the normal range
 - \circ renal function: serum creatinine ≤ 1.25 times the upper limit of the normal range
- 7. Negative infectious disease screen (hepatitis B, C or HIV); and drugs of abuse (negative urine screen).
- 8. A female patient of childbearing potential (not surgically sterlized and less than one year postmenopausal) must have a negative pregnancy test (urine human chorionic gonadotropin) at entry (prior to injection) and must have used medically accepted contraception for at least one month prior to treatment. Women of childbearing potential and men must be advised to use a medically accepted method of contraception for at

NAME OF COMPANY: jCyte, Inc	SUMMARY TABLE	(For national Authority Use Only)
NAME OF FINISHED PRODUCT:	Volume:	
jCell	Page:	

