9.0 SAFETY CONSIDERATIONS

9.1 Adverse Events

An AE is defined for this study as any untoward medical occurrence in a subject who is administered clinical study material. The occurrence of this event does not necessarily have a causal relationship with study product. An AE can therefore be any unfavorable and unintended sign (including an abnormal laboratory finding), symptom, or disease temporally associated with the use of a study (investigational) product, whether or not related to the study product.

Examples of an AE include:

- Exacerbation of a chronic or intermittent pre-existing condition, including either an increase in frequency or intensity of the condition
- Significant or unexpected worsening or exacerbation of the condition/indication under study (RP)
- A new condition detected or diagnosed after study product administration even though it may have been present prior to the start of the study
- Signs, symptoms, or clinical sequelae of a suspected overdose of either study product or a concurrent medication
- Pre- or post-treatment events that occur as a result of protocol-mandated procedures
- Antibody development

An AE does not include:

- Medical or surgical procedures (e.g., colonoscopy or biopsy); the medical condition that leads to the procedure is an AE
- Social or convenience hospital admissions where an untoward medical occurrence did not occur
- Day-to-day fluctuations of a pre-existing disease or conditions present or detected at the start of the study that do not worsen
- The disease/disorder being studied (RP), or expected progression, signs, or symptoms of the disease/disorder being studied unless more severe than expected for the subject's condition

All AEs that occur after informed consent is signed will be recorded in the source documents and on the appropriate CRF page. The information to be collected includes the nature, date and time of onset, intensity (mild, moderate, severe, life-threatening, death), duration, causality (relationship to investigational product), and outcome of the event. Even if the AE/SAE is assessed by the Investigator as not reasonably attributable to study product, its occurrence must be recorded in the source documents and on the appropriate page of the CRF.

Treatment-emergent AEs will be defined as AEs that occur after the treatment with jCell.

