9.2 Serious and Unexpected Adverse Events

A serious adverse event is one which:

- is fatal or life threatening,
- is permanently or significantly disabling, or

• requires in-patient hospitalization or prolongation of hospitalization

An unexpected adverse experience is one which:

- is not previously reported with the agents or procedures being undertaken, or
- is symptomatically and pathophysiologically related to a reported toxicity but differs because of greater severity or increased frequency.

Important medical events that may not result in death, be life-threatening, or require hospitalization may be considered an SAE when, based upon appropriate medical judgment, they may jeopardize the subject and may require medical or surgical intervention to prevent one of the outcomes listed in the above definition.

The Investigator must report all SAEs and all deaths to the study sponsor or designee immediately by telephone and in writing within five (5) days. A toll free number and an SAE reporting form to report such events will be provided. See also section 11 with respect to administrative responsibilities.

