11.0 ADMINISTRATIVE CONSIDERATIONS

11.1 Adverse Experiences

All adverse experiences (AE) must be recorded and reported to the sponsor. Any serious and unexpected AE will be reported to the sponsor or designee immediately by telephone and subsequently in writing within five (5) days. The Investigator must also notify the institutional IRB/EC. A full report, including clear photocopies of hospital records, consultants' reports, autopsy findings where appropriate, and a summary of the outcome by the Investigator, including his opinion of study relationship or attribution, will be furnished to the study Sponsor or designee as soon as practicable. It is the sponsor's responsibility to notify the FDA, other regulatory agencies as appropriate, and all clinical sites in compliance with regulatory requirements.

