If ≥ 2 subjects develop the same CTCAE grade 3 adverse events or 1 subject develops a CTCAE grade 4 adverse events, the study will be suspended until the DSMB reviews the events and makes a determination whether to continue. If a Grade 3 or worse event is clearly attributable to a non-treatment event and therefore not a suspected adverse reaction, the event will not be considered for the purposes of stopping.

The schedule of observations and assessments during the study are summarized in Table 2 of the study protocol.

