10.2 Adverse Events

All adverse event summaries will be restricted to Treatment Emergent Adverse Events (TEAE), which are defined as those AEs that occurred after dosing and those existing AEs that worsened during the study. If it cannot be determined whether the AE is treatment emergent due to a partial onset date then it will be counted as such. Verbatim terms on case report forms will be mapped to preferred terms and system organ classes using the Medical Dictionary for Regulatory Activities (MedDRA) (version 18.1).

Each adverse event summary will be displayed by treatment group. Summaries that are displayed by system organ class and preferred terms will be ordered by descending order of incidence of system organ class and preferred term within each system organ class. Summaries of the following types will be presented:

- Subject and event incidence of TEAEs by MedDRA system organ class and preferred term.
- Subject incidence of TEAEs by MedDRA system organ class, preferred term, and highest severity. At each level of subject summarization a subject is classified according to the highest severity if the subject reported one or more events. Categories of severity will be "Mild", "Moderate", "Severe" and "Life Threatening" in this summary. The "Life Threatening" column will only be shown if at least 1 life-threatening AE is reported. If any AEs are reported with missing severity, then a footnote will be added to indicate how many AEs with missing severity were reported.
- Subject and event incidence of related TEAEs by MedDRA system organ class and preferred term. Related AEs are those reported as "Related", "Possibly Related" or relationship was not reported. At each level of subject summarization a subject is classified according to the closest relationship if the subject reported

one or more events. AEs with a missing relationship will be considered related for this summary.

• Subject and event incidence of serious TEAEs by MedDRA system organ class and preferred term.

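### Non-serious CTCAE grade 3 events count toward suspending the study, but they have no reporting deadline and no stated link to the severity scale that is recorded

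*Protocol*

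**What the plan says.** **The trigger.** The Protocol Synopsis (Methodology) applies when two or more "patients develop the same CTCAE grade 3 adverse event or 1 patient develops a CTCAE grade 4 adverse event". In that case "the study will be suspended until the DSMB reviews the events and makes a determination whether to continue". SAP Section 3 repeats the rule. Both texts leave out events of grade 3 or worse that are clearly due to something other than the treatment. Neither requires an event to be serious, and neither confines the count to one site, cohort or dose level.

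**Reporting.** Protocol 9.2: "The Investigator must report all SAEs and all deaths to the study sponsor or designee immediately by telephone", with a written report inside five days. Protocol 11.1 opens by requiring that all adverse experiences be recorded and reported to the sponsor, without a time limit. It then sets one for a narrower class: "Any serious and unexpected AE will be reported to the sponsor or designee immediately by telephone", again followed in writing inside five days. AEs are entered in source documents and on the CRF (9.1). Monitors check the CRFs at visits whose frequency is not given (11.4).

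**Severity data.** Protocol 9.1 lists the items collected for each AE, among them "intensity (mild, moderate, severe, life-threatening, death), duration, causality". CTCAE grade is not listed. The adverse event listing in the SAP (16.2.7.1) likewise shows severity in words. CTCAE is mentioned only in the Protocol Synopsis, SAP Section 3 and the SAP abbreviations list.

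**The concern.** A suspension rule works only as fast as the information that reaches whoever counts the events. Here the rule is keyed to CTCAE grade and the deadlines are keyed to seriousness. These are different attributes: a severe event managed in the clinic can be grade 3 without meeting any of the seriousness criteria in 9.2.

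Two sites could therefore each hold one non-serious grade 3 event of the same kind, both fully compliant, before the sponsor has a dated obligation that brings the two together. No passage names a role that keeps the count across sites. Safety is the primary objective, Section 1.3 describes prior human data as very limited, and this is the plan's only quantified safety stop. At stake is whether the next subject is injected before anyone recognises that the condition for suspension has been met.

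**Working it through.** The documents give no figure to reproduce here, so the main check sets the rules side by side.

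| Event (not clearly due to a non-treatment cause) | Counts toward suspension? | Time limit for reaching the sponsor |
|---|---|---|
| Grade 3, serious | Yes, with a second matching event | 9.2: by phone at once, written within five days. 11.1: the same, but only if also unexpected |
| Grade 3, not serious | Yes, with a second matching event | None. 11.1 requires a report but sets no deadline |
| Grade 4 | Yes, one is enough | 9.2 applies if grade 4 is read as the protocol's life-threatening category |

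The second row is the gap. It matters only when at least one of the two matching events is non-serious; the documents do not say how often that would be.

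**Do other steps close it?**
- The check at study-number assignment (Protocol 5.0) covers only the interval between treatments.
- The four-week wait after the first Cohort 1 subject looks for serious injection-related events (3.1.1), so it is keyed to seriousness as well.
- Scheduled DSMB reviews follow Cohort 1 dose levels (Synopsis, Safety). None is scheduled within a level, and none is described for Cohort 2 data.
- The Synopsis promises continuing review of clinical safety data but gives no reviewer, frequency or data source.

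**Room for further injections in Cohort 1.** Input: one-week minimum spacing (3.1.1). The lag L, in days from the second event to its recognition, is my assumption. Spacing alone allows floor(L/7) injections:
- L = 7: 1
- L = 14: 2
- L = 28: 4

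Dose-level structure lowers the last figure. The four-subject levels put four weeks between their first two subjects, so at most subjects 2, 3 and 4 of a level fit into 28 days. The other levels have three subjects. The ceiling within one level is therefore 3. If both events arise in the first two subjects of the level being dosed, the remainder is 4 − 2 = 2 or 3 − 2 = 1.

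**Cohort 2.** No interval is required (3.1.2), so spacing sets no limit within a level of 4 or 3.

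**How often could it arise?** The documents give no event rate. Let p be the per-patient probability of one given grade 3 event that is not excluded. With N = 2 × (4 + 4 + 3 + 3) = 28, P(at least 2) = 1 − (1 − p)^28 − 28p(1 − p)^27.

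| Assumed p | P(at least 2 of 28) |
|---|---|
| 0.02 | 10.7% |
| 0.05 | 41.2% |
| 0.10 | 78.5% |
| 0.20 | 98.5% |

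These are chances that the grade 3 limb is met at all, not that it is recognised late.

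**Same site or different sites?** The Synopsis names two centers. If exactly two of 28 patients are affected, independently of site, the chance that they are at different sites is ab/C(28,2), with C(28,2) = 378. Site sizes a and b are assumed:
- 14 and 14: 196/378 = 51.9%
- 10 and 18: 180/378 = 47.6%
- 7 and 21: 147/378 = 38.9%

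**The case against.** The strongest reply is that nothing is hidden from the sponsor. Section 11.1 requires all AEs to be reported, and safety data are under continuing review. This stands: what is missing is a deadline, not a duty. A reader might infer that grade 3 events would go unseen and that dosing would carry on through a period of suspension. The documents do not support that. They state no lag, and continued dosing is only an inference from the absence of a procedure.

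Second, much of the rule is already served. Life-threatening events are serious under 9.2, so the grade 4 limb is largely covered. The important-medical-event clause in 9.2 will bring in some grade 3 events, though by judgment. This stands and confines the point mainly to the grade 3 limb.

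Third, a reader might infer from the difference between 9.2 and 11.1 that a known injection complication could escape prompt reporting even when serious. It could not if the site follows 9.2, which covers every SAE; doing so also satisfies the reporting time limit in 11.1. The texts differ and need reconciling, but the difference does not defeat the rule.

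Fourth, the Cohort 2 exposure is partly a spacing choice. With no minimum interval, a whole level could be injected before any event occurs, however fast reporting is. That also stands. DSMB review of the same dose level in Cohort 1 comes first, which limits the risk further.

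Fifth, the five intensity words are ordered, and a footnote to SAP Table 14.3.1.2 calls them a grade. A mapping may be intended, but none is written.

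Finally, Section 8.2.2 contains another halt, for faster deterioration of the injected eye on ERG and BCVA. It has no numerical criterion and does not address grade 3 events generally.

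**Conclusion.** The point holds in a limited form and should be fixed. A non-serious grade 3 event counts toward suspension, yet no reporting deadline applies to it, and the recorded severity scale has no stated correspondence to the grades in the rule. Compliance with the reporting sections therefore does not ensure that a met trigger is recognised in time.

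The effect is a possible delay, chiefly within a Cohort 1 dose level and in Cohort 2. Its size depends on a lag that the documents do not give. Assumed lags of 7 to 28 days leave room for one to three further Cohort 1 injections within a level, and fewer when little of the level remains. The event rates and site splits used above are also assumptions.

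The conclusion rests on the supplied text; the AE form and the study procedure manual are not part of it. The rule's absence from the numbered protocol sections is housekeeping, because the Synopsis is part of the protocol.

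**What to change.** Leave the suspension rule unchanged.

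1. State in the AE reporting sections that any event that could count toward the rule goes to the sponsor on the existing expedited timeline, whether or not it is serious. Name the role that keeps the count across sites.
2. Record the CTCAE grade on the AE form, or state in 9.1 how the five intensity words correspond to grades.
3. Reconcile 9.2 and 11.1, which differ on which serious events are reported immediately.

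As housekeeping, repeat the rule in the numbered sections of the protocol. The cost is some protocol wording, one form field or one sentence of mapping, and a few additional expedited reports in a trial of up to 28 subjects.

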4.3 Subject Withdrawal Criteria

Subjects may withdraw from the study at any time. Subjects may be discontinued from the study for any of the following reasons:

- Withdrawal of consent by the subject
- Development of intolerable AEs during the study
- Major protocol violation
- Lost to follow-up
- Any event that prevents the subject from meeting the study requirements

The investigator may also withdraw a subject at any time at his/her discretion. The sponsor reserves the right to terminate the study or withdraw any subject from the study for any reason at any time.

In addition, the sponsor reserves the right to temporarily suspend or prematurely discontinue this study either at a single site or at all sites at any time and for any reason. If such action is taken, the sponsor will discuss this with the investigator (including the reasons for taking such action) at that time. The sponsor will promptly inform all other investigators and/or institutions conducting the study if the study is suspended or terminated for safety reasons, and will also inform the regulatory authorities of the suspension or termination of the study and the reason(s) for the action. If required by applicable regulations, the investigator must inform the IRB promptly and provide the reason for suspension or termination.

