8.2.2 Electroretinogram (ERG)

ERG examinations will be performed according to ISCEV standards and standardized among clinics to minimize difference between centers: briefly, patients are dark adapted for 30 min, electrodes attached under dim red illumination (dark room safe light). ERG responses will be recorded using single scotopically-balanced dim blue and red light flashes, and bright white flashes per detailed protocol. ERG at 6, 12 months are compared to pre-injection in terms of 1) a-wave amplitude, 2) b-wave amplitude, 3) time from flash onset to a wave trough and 4) time from flash onset to b-wave peak. In individual patients significantly faster deterioration of injected eye by ERG parameters and BCVA will halt further enrollment, although the latter measure is likely to be the more informative.

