· ·								
System Organ Class 2	n (%)	n (%)	n (%)	n (%)	n (%)	n (%)	n (%)	n (%)
Preferred Term 1	n (%)	n (%)	n (%)	n (%)	n (%)	n (%)	n (%)	n (%)
Preferred Term 2	n (%)	n (%)	n (%)	n (%)	n (%)	n (%)	n (%)	n (%)

Note: At each level of summation (overall, system organ class, preferred term), subjects reporting more than one adverse event are counted only once using maximum severity grade. path\t_program.sas date time

jCyte, Inc. Protocol: JC-01

Table 14.3.1.2 TEAEs by System Organ Class, Preferred Term and Maximum Severity Safety Population

				Coho	rt 2							
		0.5 x 10	⁶ hRPC							Tota	ıl ^[1]	
System Organ Class /		(N	=)							(N=	-)	
Preferred Term	Mild	Moderate	Severe	Life	Mild	Moderate	Severe	Life	Mild	Moderate	Severe	Life
				Threatening				Threatening				Threatening
Subjects Reporting at Least One TEAE	n (%)	n (%)	n (%)	n (%)	n (%)	n (%)	n (%)	n (%)	n (%)	n (%)	n (%)	n (%)
System Organ Class 1	n (%)	n (%)	n (%)	n (%)	n (%)	n (%)	n (%)	n (%)	n (%)	n (%)	n (%)	n (%)
Preferred Term 1	n (%)	n (%)	n (%)	n (%)	n (%)	n (%)	n (%)	n (%)	n (%)	n (%)	n (%)	n (%)
Preferred Term 2	n (%)	n (%)	n (%)	n (%)	n (%)	n (%)	n (%)	n (%)	n (%)	n (%)	n (%)	n (%)
· ·												
System Organ Class 2	n (%)	n (%)	n (%)	n (%)	n (%)	n (%)	n (%)	n (%)	n (%)	n (%)	n (%)	n (%)
Preferred Term 1	n (%)	n (%)	n (%)	n (%)	n (%)	n (%)	n (%)	n (%)	n (%)	n (%)	n (%)	n (%)
Preferred Term 2	n (%)	n (%)	n (%)	n (%)	n (%)	n (%)	n (%)	n (%)	n (%)	n (%)	n (%)	n (%)

^[1] Total includes both Cohorts 1 and 2.

Note: At each level of summation (overall, system organ class, preferred term), subjects reporting more than one adverse event are counted only once using maximum severity grade. path/t program.sas date time

Table 14.3.1.3 Related to Study Drug TEAEs by System Organ Class and Preferred Term Safety Population

		Coh	ort 1		Cohort2					
System Organ Class /	0.5 x 10	⁶ hRPC			0.5 x 10 ⁶	hRPC			Tota	ıl ^[1]
Preferred Term	(N	=)	(N:	=)	(N=		(N	[=)	(N=)	
	Subjects	Events	Subjects	Events	Subjects	Events	Subjects	Events	Subjects	Events
Subjects Reporting at Least One Related TEAE	n (%)	XX	n (%)	XX	n (%)	xx	n (%)	xx	n (%)	xx
System Organ Class 1	n (%)	XX	n (%)	XX	n (%)	XX	n (%)	XX	n (%)	XX
Preferred Term 1	n (%)	XX	n (%)	XX	n (%)	XX	n (%)	XX	n (%)	XX
Preferred Term 2	n (%)	XX	n (%)	XX	n (%)	XX	n (%)	XX	n (%)	XX
System Organ Class 2	n (%)	XX	n (%)	xx	n (%)	XX	n (%)	XX	n (%)	XX
Preferred Term 1	n (%)	XX	n (%)	XX	n (%)	XX	n (%)	XX	n (%)	XX

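### The suspension rule names grade 4 but not grade 5, so read literally a treatment-related death with no preceding grade 4 event does not force suspension

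*Protocol*

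**What the plan says.** The Methodology part of the protocol synopsis holds the only rule that makes suspension mandatory on the basis of adverse events. Its first limb needs at least two patients with the same CTCAE grade 3 event. Its second limb reads "1 patient develops a CTCAE grade 4 adverse event, the study will be suspended until the DSMB reviews the events". The sentence after it is an exemption, which opens "If a Grade 3 or worse event is clearly attributable to a non-treatment event" and removes such events from the count when they are not suspected adverse reactions. SAP section 3 restates both sentences; its second limb reads "1 subject develops a CTCAE grade 4 adverse events, the study will be suspended until the DSMB reviews the events".

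Protocol section 9.1 has each event recorded with its "intensity (mild, moderate, severe, life-threatening, death"). Death is therefore a level of its own, above life-threatening. SAP section 10.2 stops one level lower: "Categories of severity will be 'Mild', 'Moderate', 'Severe' and 'Life Threatening' in this summary". The layout of Table 14.3.1.2 has the same four columns and notes that "subjects reporting more than one adverse event are counted only once using maximum severity grade".

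**The concern.** A suspension rule should be at least as strict for a worse outcome as for a lesser one. Here the wording runs the other way at the top of the scale. A single related grade 4 event stops the study until the DSMB has ruled. A related event whose only high grade is 5 satisfies neither limb.

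Safety and tolerability are the primary objective, and this is the one automatic brake tied to adverse events. If it does not reach a death, the decision to pause rests on the judgement of the sponsor or investigator at the moment when a pre-specified rule is most useful. The same level is also missing from the SAP's severity summary, so a fatal event has no column there.

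**Working it through.** The plan attaches no error rate or other operating figure to this rule, so there is nothing to reproduce. The check is logical.

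**Step 1. Apply the rule to sets of related events.** All events in a row are of the same type, in different patients. One assumption is needed: neither document maps the section 9.1 labels to CTCAE grades. I take the five labels in order as grades 1 to 5, so death is grade 5. The amended rule changes only the second limb, to grade 4 or worse.

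| Grades recorded | Rule as written | Amended rule |
|---|---|---|
| one grade 3 | no | no |
| two grade 3 | yes, first limb | yes, first limb |
| one grade 4 | yes, second limb | yes, second limb |
| one grade 5 | **no** | yes, second limb |
| two grade 5 | **no** | yes, second limb |
| one grade 3 and one grade 5 | **no** | yes, second limb |
| one grade 4 and one grade 5 | yes, second limb | yes, second limb |

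The rows that change are those with a grade 5 event, no grade 4 event and fewer than two of the same grade 3 event. Changing the second limb repairs all of them, so the first limb can stay as it is.

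**Step 2. Look for another provision that forces suspension after a death.**

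- Protocol 8.2.2 is mandatory ("significantly faster deterioration of injected eye by ERG parameters and BCVA will halt further enrollment"), but it concerns retinal function and acuity.
- Protocol 4.3 is a power, not a duty: "the sponsor reserves the right to temporarily suspend or prematurely discontinue this study". Section 3.4 likewise permits termination without requiring it.
- Protocol 9.2 and 11.1 govern reporting. Deaths go to the sponsor immediately by telephone, but neither section says that treatment stops.
- Protocol 3.1.1 holds subject 2 for at least four weeks, to confirm that subject 1 has had no serious injection-related event. Section 9.2 counts a fatal event as serious, so a related death in subject 1 during that interval blocks subject 2. Later subjects at that dose level are at least a week apart, with checks on days 1, 2 and 3; no pause is specified for a later death.
- The synopsis places formal DSMB reviews after each Cohort 1 dose level, before the next level in Cohort 1 and before the same level in Cohort 2. These gate movement between levels, not treatment within one.
- Protocol 3.1.2 sets no minimum interval in Cohort 2 once the relevant Cohort 1 data are acceptable.

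No provision closes the gap for a related death after the first subject but within a dose level, or for one in Cohort 2.

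**Step 3. Weigh the exemption clause.** An exemption is needed only for events that would otherwise count. Because it covers grade 3 or worse, it points to a trigger that was meant to be open at the top. But grade 4 alone already satisfies *or worse*, so the clause does not settle the matter.

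**Step 4. Compare the severity scales.** Section 9.1 has five levels, ending in death. SAP 10.2 and Table 14.3.1.2 have four, ending in life-threatening. The footnote for missing severity does not help, because a severity of death is not missing. The table would have to omit the event or show it one level too low.

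**The case against.** The strongest reply is that the rule fires when a patient develops a grade 4 event, and does not require grade 4 to be the highest or final grade. A patient who dies of a treatment complication will often have passed through a life-threatening stage, and that stage already triggers suspension. This stands, and it narrows the gap to a related death with no preceding grade 4 event. It does not remove it: neither document says how the earlier grades of a fatal event are recorded, and section 9.1 makes death a separate entry.

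A second reply is that any DSMB or sponsor would read grade 4 as a floor, helped by the exemption clause, and that the other controls are substantial. That is probably right in practice, and it is why the risk is low. It still relies on readers to supply a grade that the rule omits.

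A third reply is that the severity table is a layout matter. SAP Appendices A and B allow tables to be reorganised during programming, and the life-threatening column already appears only when needed. This stands, and that part is minor. It is also fair that the SAP, dated 08Nov2017 against a stated study period of 2015-2016, does not govern suspension. Amending it is for consistency and protects no subject by itself.

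A reader might go further and infer that the plan would let the study carry on after a related death, or that the SAP would hide one. The documents support neither. Deaths must be reported at once and the sponsor can suspend at any time. A fatal event is serious under the SAP's own definition, so a treatment-emergent death would appear in the serious event table, and deaths also have a place in the disposition table and the listings.

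**Conclusion.** The concern holds as a wording defect in a decision rule. Read literally, the only mandatory suspension rule based on adverse events does not fire for a treatment-related death with no preceding grade 4 event, although it fires for a single related grade 4 event. No other provision makes suspension automatic for such a death later within a dose level or in Cohort 2.

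The practical risk is low. The documents give no rate for related deaths, so I put no probability on reaching the gap. The conclusion assumes that death corresponds to CTCAE grade 5 and that no grade 4 event preceded it. That deaths were meant to count is strongly suggested by the exemption clause, but not proved. The severity-table mismatch is real and secondary. The protocol wording should be corrected because it is the study's automatic safety brake and the correction costs almost nothing.

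**What to change.** In the protocol synopsis, change the second limb to: *1 patient develops a CTCAE grade 4 or worse (grade 4 or 5) adverse event*. Mirror it in SAP section 3. Leave the first limb and the exemption as they are.

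As a minor consistency change, add a death (fatal) category to the SAP 10.2 severity summary and to Table 14.3.1.2, shown only if at least one such event is reported, as is already done for life-threatening events.

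The cost is one phrase in each document and one conditional table column, with no new visits or data. Needless suspensions are not a concern, because deaths clearly due to something other than treatment remain exempt.
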